## REVISION HISTORY

Revision #	Version Date	Summary of Changes	Consent Change?
1	10/03/2017	detailing recruitment methods, consent process, inclusion/protection of vulnerable populations	No
2	05/14/2018	Adding new recruitment site: Boynton Health Services	Yes
3	08/02/2018	Changing title, new K01 funding	Yes
4	08/30/2018	Adding sample size to 50	No
5	12/10/2018	Adding assessment tasks, hotline information cards, and expanding inclusion	Yes
6	05/01/2019	More detailed plan in case of acute mental health. Compensation no longer mentioned under benefits section.	No
7	04/09/2019 Re-submitted 05/14/2019	Recruitment changes under the CAR Recruitment Registry, increasing sample size to 70, adding an acceptable time window for completion of follow-up visits, and indicating participants will be compensated with ClinCard.	No
8	06/06/2019	Addition of an MRI scan at ~1-month follow-up with updated compensation. Addition of optional saliva collection for genotyping. Exclusion criteria regarding psychiatric diagnosis changed to only exclude those with psychosis. Modify definition of follow-up visits with more flexible timepoints. Indication of how data will be collected for missed visits. Removal of Boynton as a recruiting site. Addition of optional informed consent to communicate through unencrypted email and/or	Yes

PROTOCOL TITLE: *Effects of Neuromodulation and Cognitive Training on Brain Networks Associated with Relapse in Alcohol Use Disorder*  
 VERSION DATE: 10-25-2021

9	08/05/2019	Addition of form to assess and record more detailed understanding of informed consent	Yes
10	02/19/2020	Increase number of consented participants to 100. Test for alcohol use at in-person follow-up visit on an as-needed basis.	Yes
11	04/08/2020	COVID19: Only during the COVID19 crisis, research staff will take subject material home.	No
12	05/08/2020	Addition of optional decision-making computerized task; Option to complete follow-up assessments remotely; Updated Set Shifting task stimuli.	Yes
13	09/10/2020	Modifications related to COVID19 crisis, statement saying study will follow Sunrise Plan; Addition of research-dedicated room in Lodging Plus treatment program.	Yes
14	03/09/2021	Modifications related to routine audit. Modifications related to optional ecological momentary assessment (EMA) survey.	Yes
15	06/03/2021	Parking reimbursement for participants	Yes
16	08/31/2021	Modification related to maintaining COVID19 changes permanently, for having the option of either in-person or remote visits.	Yes, only change is new lab phone number

17	10/25/2021	To directly collect EMA data on factors that can mediate clinical outcomes (influencing Aims 2 and 3), participants will be given the option of using a wearable device that passively tracks stress and sleep when they leave the addiction treatment program. Passive data collected from the wearable device will be useful to complement and compare with the self-report EMA data collected through surveys.	Yes
----	------------	---	-----

## ABBREVIATIONS/DEFINITIONS

- DLPFC - Dorsolateral Prefrontal Cortex
- NAcc - Nucleus accumbens
- FC - Functional connectivity
- AUD - Alcohol use disorder
- fMRI - Functional magnetic resonance imaging
- tDCS - Transcranial direct current stimulation
- CMRR - Center for magnetic resonance research
- HCP - Human Connectome Project

## STUDY SUMMARY

Study Title	Effects of Neuromodulation and Cognitive Training on Brain Networks Associated with Relapse in Alcohol Use Disorder
Study Design	Double-blind, within subject, and sham-controlled
Primary Objective	The overall objective of this proposal is to enhance FC between DLPFC and NAcc as a therapeutic intervention to enhance cognitive flexibility.
Secondary Objective(s)	Reduce craving in addiction.
Exploratory Objective(s)	Explore associations between genotype/epigenetic changes and intervention response.
Research Intervention(s)/ Investigational Agents	Transcranial direct current stimulation and magnetic resonance imaging.
IND/IDE # (if applicable)	N/A
Investigational Drug Services # (if applicable)	N/A
Study Population	Individuals with alcohol use disorder
Sample Size (number of participants)	100 consented
Study Duration for Individual Participants	8 months, up to 4-month extension available depending on participant availability for follow-ups

## 1. Objectives

2. The overarching goal of this project is to expand the traditional expertise in non-invasive neuromodulation at the University of Minnesota towards developing novel paired-neuromodulation approaches using tDCS for new addiction treatments that support long-term abstinence. This study will allow us to investigate whether the pairing of DLPFC stimulation and cognitive flexibility training can enhance FC between DLPFC and NAcc. We have identified higher FC between DLPFC and NAcc in alcoholics that have successfully maintained abstinence for extended periods of time (7 years). This paired-neuromodulation approach can potentially be used as a therapeutic intervention to decrease relapse probability in addiction. The long term goal is to develop new addiction treatments that support long-term abstinence. The overall objective of this proposal is to enhance FC between DLPFC and NAcc as a therapeutic intervention to enhance cognitive flexibility and reduce craving in addiction.
3. Exploratory objectives: To associate genotypes and epigenetic changes with variations in intervention response and clinical outcome.

## 2. Background

1. Significance of Research Question/Purpose: The relapsing nature of alcoholism is a major obstacle to successful treatment. About 60% of those entering treatment will relapse within one year. To improve treatment outcome, new interventions targeting the underlying brain biomarkers of relapse vulnerability hold significant promise in reducing this critical public health problem.
2. Preliminary Data: Using resting functional magnetic resonance imaging (fMRI) we have identified brain biomarkers that support long-term abstinence. Our cross-sectional and longitudinal findings provide evidence that higher functional connectivity (FC), particularly between nucleus accumbens (NAcc) and dorsolateral prefrontal cortex (DLPFC), is a potential brain biomarker that supports abstinence. Long-term abstinent alcoholics (7 years of abstinence) have higher resting FC between NAcc and DLPFC when compared to controls. Short-term abstinent alcoholics (11 weeks of abstinence) have intermediate FC (lower than long-term abstinent alcoholics and higher than controls) (Camchong, Stenger, and Fein 2013c, [a] 2013). Further, lower FC between NAcc and DLPFC at 11 weeks of abstinence can be a predictor of subsequent relapse (with 74% accuracy) (Camchong,

Stenger, and Fein 2013b). Moreover, in a pilot longitudinal FC study examining resting FC of NAcc at 5 and 13 weeks of abstinence in individuals with substance use disorder, we found that FC between NAcc and DLPFC decreased from 5 to 13 weeks of abstinence in subsequent relapsers, while it increased in subsequent abstainers (Camchong et al. 2014). Based on the above, we believe that long-term abstinence is supported by a compensatory mechanism that mediates proper executive function over reward (mediated by DLPFC-NAcc FC), a potential brain biomarker that could be an intervention target. These findings provide a compelling case to explore whether this brain biomarker can be modulated to enhance patients' ability to remain abstinent. There is a need to investigate methods that can be used to increase FC between DLPFC and NAcc.

3. Existing Literature: Cognitive flexibility, the ability to change maladaptive behavior, depends on DLPFC input to NAcc (Gruber, Hussain, and O'Donnell 2009). DLPFC transmits reward representations to NAcc through glutamatergic projections that guide goal-directed behavior (Ballard and Knutson 2009). If DLPFC fails to activate when required, a common observation in substance use disorder, target neurons in the NAcc core do not receive critical information needed to select the appropriate outcome, causing acquired maladaptive response patterns to persist (e.g. drug consumption) (Gruber, Hussain, and O'Donnell 2009). Higher FC between DLPFC and NAcc may be achieved by stimulating DLPFC while subjects perform a task that requires cognitive flexibility, the reversal learning task. Transcranial direct current stimulation (tDCS) is a non-invasive brain stimulation technique that can modulate brain connectivity. DLPFC stimulation may increase input to NAcc to facilitate proper selection of goal-directed behavior and may also decrease craving in individuals with substance use disorder (Boggio et al. 2008). Genetics and treatment response: A source of treatment response variability could stem from differences between participants in baseline genetic profiles or epigenetic changes over the course of treatment. Genetic polymorphisms, especially in genes important for neuroplasticity, may also mediate neuroplastic changes underlying the effects of tDCS (Chhabra et al., 2016), as has been demonstrated with gene BDNF (Antal et al., 2010; Fritsch et al., 2010). In light of these genetic influences on key tenants of our study - i.e. treatment response in alcohol use disorder and physiological effects of tDCS - we will collect genetic samples from participants to determine whether genetic or epigenetic variations may affect

response to the cognitive training and tDCS intervention. This information may help inform the development of more individually-tailored treatment protocols in the future. As this is a secondary aim, participants will be given the choice in the consent form to opt in or out of the genetic sampling procedure.

4. There is preclinical data suggesting that sleep alterations are associated with increased alcohol consumption (Garcia-Garcia et al 2021). We have preliminary clinical data showing that sleep alterations are associated with vulnerability to relapse. The nature of these associations may be specific to an individual, so that not enough sleep or too much sleep can be associated with relapse vulnerability depending on the individual. Moreover, sleep alterations, which are common in alcohol use disorder are associated with brain alterations (Zhang et al 2021). It is important to determine whether sleep disturbances are a factor that affects treatment outcome in alcohol use disorder.

### **3. Study Endpoints/Events/Outcomes**

1. Primary Endpoint/Event/Outcome: In a double-blind randomized design, 100 abstinent (~2 weeks abstinent) individuals with alcohol use disorder (AUD) recruited from Lodging Plus Program will receive 10 sessions (2 sessions per day for 5 days) of either (i) transcranial direct current stimulation (tDCS) to the PFC or (ii) sham-tDCS. All subjects will perform the reversal learning task during tDCS intervention (active or sham) to prime the engagement of the NAcc-PFC brain circuit that mediates cognitive flexibility. Rest fMRI and craving measures will be collected before the first and after the last day of tDCS sessions, and about one month after the last fMRI (timepoint depending on participant availability). Monthly follow-up interviews will be conducted for approximately 8 months after intervention completion to query relapse status. Dependent variables will be (i) change in NAcc-PFC FC between 2,3 weeks of abstinence and one month later, (ii) change in craving scores between 2 and 3 weeks of abstinence and (iii) relapse status ~8 months after study participation. Aim 1: To investigate whether NAcc-PFC FC can be modulated, we will compare magnitude and durability of change in NAcc-PFC FC between active-tDCS and sham-tDCS groups. Aim 2: To determine if PFC stimulation has a short-term effect on behavior related to clinical outcome, we will compare change in craving scores (difference in craving scores between 2 and 3 weeks of abstinence) between active-tDCS and sham-

tDCS groups. Aim 3: To correlate neuromodulation intervention with long-term clinical outcome, we will record craving and relapse status during the ~8 months following treatment discharge. We will examine the relationship between change in NAcc-PFC FC between 2 and 3 weeks of abstinence and subsequent (i) monthly craving scores and (ii) relapse status. Aim 4: Examine relationships between genetic variants, epigenetic changes and treatment outcome (e.g. durability, functional connectivity).

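### Section 3 lists FC change, craving change and relapse unranked under its only heading, the primary one, and no other section settles which single result is primary

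*Combined protocol and SAP*

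**What the plan says.** **Section 3 (Study Endpoints/Events/Outcomes)** has a single numbered item. It opens "Primary Endpoint/Event/Outcome: In a double-blind randomized design" and runs on through design, outcomes and Aims 1 to 4. There is no secondary or exploratory heading. The outcomes begin "Dependent variables will be (i) change in NAcc-PFC FC", over a window that takes in 2 and 3 weeks of abstinence and a point one month later, and continue "ii) change in craving scores between 2 and 3 weeks of abstinence and (iii) relapse status ~8 months after study participation". Under Aim 1, "we will compare magnitude and durability of change in NAcc-PFC FC between active-tDCS and sham-tDCS groups".

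**The Study Summary** ranks its objectives. The primary is: "The overall objective of this proposal is to enhance FC between DLPFC and NAcc as a therapeutic intervention to enhance cognitive flexibility". The secondary is: "Reduce craving in addiction". Genetics is exploratory. Relapse is not among the objectives.

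**Section 1 (Objectives)** states one overall objective that covers FC, cognitive flexibility and craving together.

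**Section 5 (Procedures Involved, Study Design)** repeats much of Section 3. There, FC change covers only the interval from 2 to 3 weeks of abstinence, and Aim 1 compares magnitude without durability. Relapse as a dependent variable is followed for 6 months, although Aim 3 in the same section says about 8.

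**Section 16 (Data Management, Data Analysis Plan)** applies one mixed-model analysis of variance to FC and craving before and after the intervention. It adds a repeated-measures analysis of monthly data over 6 months, and a log-rank test presented as the means of establishing efficacy of active over sham. It gives no primary test, order of testing, alpha or multiplicity rule. It calls the study a pilot to which a power analysis does not apply.

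**The concern.** The section that defines the endpoints puts three different outcomes (a brain measure, a symptom score and a clinical event) under the word primary. The summary gives that rank to one of them only. If FC shows no difference between the arms but craving or relapse does, a report could cite Section 3 and describe the trial as positive on its primary endpoint. If FC is positive and the others are not, the report could cite the Study Summary. Either reading has support in current protocol text, so the choice could be made after the results are known.

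This does not depend on one's view of multiplicity correction in pilot studies. Naming one primary outcome in advance requires no alpha adjustment.

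**Working it through.** **Step 1. The status of each outcome, place by place.**

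| Place | FC change | Craving change | Relapse |
|---|---|---|---|
| Study Summary | primary objective, no window | secondary objective | not listed |
| Section 1 | in the one overall objective | in the same objective | not in the overall objective |
| Section 3 | primary heading; window reaches one month later; magnitude and durability | primary heading; 2 to 3 weeks | primary heading; about 8 months |
| Section 5, Study Design | dependent variable; 2 to 3 weeks; magnitude only | dependent variable; 2 to 3 weeks | dependent variable; 6 months (about 8 in Aim 3) |
| Section 16 | mixed model, before and after | same mixed model, before and after | log-rank test, event not named |

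Craving is primary, secondary or unranked depending on the section. FC is the best supported candidate for primary, but a reader who accepts it still cannot tell whether the window ends after the intervention or a month later. Section 3 also writes PFC where the Study Summary and Section 5 write DLPFC.

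**Step 2. Error rate if any of the three may count as the primary result.** The documents give no alpha, power or familywise error rate, so there is no stated figure to reproduce. Assume a two-sided 0.05 per test, no adjustment, three tests and independence:

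- one named primary: 0.05
- any of three: 1 − (1 − 0.05)³ = 1 − 0.857375 = 0.142625, or 14.3%

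**Step 3. Sensitivity to correlation.** Section 2 links FC to relapse, so independence is doubtful, but the documents give no correlations. Simulating three equally correlated, two-sided z-tests (1,000,000 draws per setting, cut-off 1.96) gives:

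- pairwise correlation 0.3: 13.6%
- pairwise correlation 0.5: 12.5%
- pairwise correlation 0.8: 9.8%

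The rate stays at about two to three times the 5% of a single primary.

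**Step 4. The alternative of keeping all three as primaries.** Bonferroni would give 0.05 / 3 = 0.0167 per test. Section 25 aims for 70 participants with complete data and Section 4 allocates half to each arm, so 35 per arm. For a difference in means, the effect detectable with 80% power, in SD units (normal approximation), is (z for alpha + 0.842) × √(2/35), where √(2/35) = 0.239:

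- alpha 0.05: (1.960 + 0.842) × 0.239 = 0.67 SD
- alpha 0.0167: (2.394 + 0.842) × 0.239 = 0.77 SD

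Power at 0.67 SD falls from 80% to 66%. These effect sizes are yardsticks only; the documents give none.

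**Step 5. Which FC contrast the documents support best.** Section 5 gives the 2 to 3 week window, and Section 16 specifies FC only before and after the intervention. With two arms and two time points, the arm-by-time interaction in that model is the active versus sham comparison of change. Section 16 sets out no one-month FC contrast.

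**The case against.** The strongest reply is that Section 3 is a study synopsis placed under a template heading. It speaks of dependent variables rather than primary endpoints. Its Aims 1, 2 and 4 follow the Study Summary's order of FC, craving and genetics. Read literally, the heading would also make the genetics of Aim 4 primary, which nobody intends. The study is described as a pilot, which lowers the stakes.

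Much of this stands. A reader might infer that the sponsor deliberately declared three co-primary endpoints. The documents do not show that; they show a ranking of objectives that was not carried into the endpoint section. The pilot label is not a complete answer, however, because Section 16 gives the log-rank test the task of establishing efficacy. Section 1 and the two FC windows also mean that the Study Summary alone does not identify one primary result.

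Three stronger readings should be set aside:

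- A reader might count four tests, treating FC magnitude and FC durability separately, and reach 1 − 0.95⁴ = 18.5%. The arithmetic is right, but Section 16 specifies no durability test, so the count comes from the wording of Aim 1 and not from the analysis plan.
- A reader might infer that Section 16 tests every listed outcome between arms. The log-rank event is unnamed, no between-arm test of relapse status at about 8 months is given, and Aim 3 relates relapse to FC change.
- A reader might suppose that making durability and relapse secondary merely restores the Study Summary. It mentions neither, so that label would be new.

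**Conclusion.** The point holds as an internal contradiction about which result is primary. Three outcomes stand unranked under the only heading in Section 3, the Study Summary ranks two of them and omits the third, and neither Section 1, Section 5 nor Section 16 settles the matter. The practical consequence is that a craving or relapse finding could be presented as the primary success beside a null FC result.

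Its size, if the three were each tested and any one could be claimed, is a 14.3% chance of at least one false positive under independence. With pairwise correlation from 0.8 to 0.3 it is about 10% to 14%. The comparison is 5% for one named primary. These figures rest on an assumed unadjusted two-sided 0.05 per test and on assumed correlations. They illustrate the latitude left open and are not error rates that the plan states. The contradiction itself depends on none of these assumptions. It should be corrected, and the pilot status keeps it below a critical fault.

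**What to change.** 1. In Section 3, name one primary outcome, window and test: active versus sham change in NAcc-DLPFC FC from before to after the intervention (2 to 3 weeks of abstinence), tested by the arm-by-time interaction in the Section 16 mixed model. The outcome follows the Study Summary. The window is the one in Section 5 and the FC contrast that Section 16 specifies.
2. List craving change as secondary, as the Study Summary does. List FC durability and relapse as secondary too, and record that this designation is new.
3. Reconcile Sections 1, 3, 5 and 16 on the objective, the FC window, the region label and the relapse horizon.
4. In Section 16, state the alpha for the primary test and say that all other tests carry no confirmatory claim. Reword the log-rank purpose accordingly and name its event.
5. Document that the change was made before any unblinded review of outcome data. The protocol is dated 10-25-2021 and expects enrolment to end in Fall 2022, so this would be a change to a running trial.

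The cost is a protocol amendment and the loss of the option to present craving or relapse as a primary success. No new data, visits or participants are needed. Keeping all three as adjusted primaries would instead cost power, as Step 4 of the working shows.

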#### 4. Study Intervention(s)/Investigational Agent(s)

1. Description: As in previous clinical studies that achieved treatment response and reduction of relapse probability (Klauss et al. 2014), patients will receive two 13 minute daily sessions with a rest interval (no stimulation) of 20 minutes in between (13:20:13 schedule; as in (Klauss et al. 2014; Monte-Silva et al. 2013)) of either active (2-mA) or sham transcranial direct current stimulation (tDCS) every day for five consecutive days. This study will add to the literature by having patients practice the reversal learning task (D'Cruz et al. 2011) during tDCS intervention, to enhance paired neuromodulation. While patients practice the reversal learning task, half of the patients will receive active tDCS stimulation to the left DLPFC to enhance top-down control and improve the tuning or gating of the extraneous information and the other half will receive sham tDCS.
2. The tDCS will be performed with Neuroelectrics Starstim Enobio 20 (Neuroelectrics Barcelona, Spain). This device has been approved for use in research without an investigational device exemption due to meeting criteria for non-significant risk. In addition, the device has built in safety mechanisms which allow for the immediate cessation of stimulation should the subject become uncomfortable or impedance levels too high. The current will be administered via two saline soaked electrode sponges (approximately 25cm^2) for two 13 minute blocks. The current strength during each administration will be 2 mA. These administration procedures are in line with other protocols that have outlined safe administration (Nitsche et al. 2008, 2007). Across more than 2000 subjects no side-effects have been reported with the exception of slight itching under the electrode and occasional occurrence of headache, fatigue, or nausea (Poreisz et al. 2007). The anodal electrode will be placed over left DLPFC and the cathodal electrode will be placed over right DLPFC.
3. Drug/Device Handling: We will use transcranial direct current stimulation (tDCS) to stimulate dorsolateral prefrontal cortex (DLPFC). TDCS is a non-

invasive brain stimulation technique that can modulate brain connectivity. TDCS involves applying a weak electrical current (2mA or less) to the scalp via anodal and cathodal electrode sponges, causing either increases or decreases in cortical excitability, respectively. Research has shown in both healthy subjects and patients (e.g. Alzheimer's disease, Parkinson's disease, stroke, and depression) that tDCS has the potential to modulate synaptic strengthening and neurotransmitter-dependent plasticity underlying changes in behavior and learning (Lang et al. 2005).

